5.0 DOSING DELAYS/DOSE MODIFICATIONS

5.1 Dose Modifications for Nivolumab and Nivolumab and Ipilimumab Combination

Participants with an overall response of SD, PR, CR, or unconfirmed PD (refer to Section 9.1 for RECIST Criteria, Section 9.2 for KS response evaluation, and Section 9.3 for the 2017 RECIL Criteria for response evaluation) at the scheduled response visits at week 8 and all subsequent visits day 1 of cycles 6 and 9 will be eligible to continue to receive study drug treatments provided that they also have an ECOG performance status score of ≤ 2 , and did not have a DLT or other safety risk requiring discontinuation of the study drugs, as defined below.

Please refer to Appendix X to the protocol for toxicity management algorithms, which include specific treatment guidelines. Where discrepancies occur between Section 5.1 and Appendix X, use the instructions in Section 5.1. These algorithms should be followed unless there are specific clinical circumstances for which the treating physician indicates variations or alternative treatment are needed.

Generally, we strongly encourage early evaluation, withholding drug, and appropriate treatment as indicated in the management tables and following event specific guidelines.

Table 2: Dose Modification Tables for Nivolumab and Nivolumab and Ipilimumab Combination

All Other Events*	Management/Next Dose for Nivolumab and Combination
≤ Grade 1	No change in dose.
Grade 2	Hold** until ≤ Grade 1 OR baseline. Resume at same dose level.
Grade 3	Hold** until ≤ Grade 1 continue at investigator discretion.
Grade 4	Off protocol therapy.

^{*} Not immunologically mediated (excluding clinically insignificant lab abnormalities, see Section 6.4.1)

Recommended management: As clinically indicated.

All Other Events**	Management/Next Dose for Nivolumab and Combination
≤ Grade 1	No change in dose.
Grade 2	Hold until \leq Grade 1 OR baseline. When resolved \leq Grade 1 and off steroids for at least 1 week, resume at same dose level.
Grade 3	Off protocol therapy (exceptions noted in 5.4). May resume nivolumab monotherapy if resolved to Grade 1 or less (off physiologic

^{**}Participants being treated on the HL expansion cohort meeting the inclusion criteria will hold therapy only if a worsening in ≥ 1 grade beyond baseline eligibility requirements occurs on the day of therapy. Participants may resume treatment when AEs are resolved or have returned to baseline. Participants requiring more than two dose delays for the same event should go off protocol therapy.

All Other Events*	Management/Next Dose for Nivolumab and Combination
	replacement doses of corticosteroids) by end of week 8. If AE occurs with nivolumab monotherapy, then off protocol therapy.
Grade 4	Off protocol therapy.
** Immunologically mediated.	
Recommended management: As clinically indicated.	

Cardiac *	Management/Next Dose for BMS-936558 (Nivolumab) + Ipilimumab Cardiac Toxicities
≤ Grade 1	Hold dose pending evaluation and observation.** Evaluate for signs and symptoms of CHF, ischemia, arrhythmia, or myositis. Obtain history EKG, CK (for concomitant myositis), CK-MB. Repeat troponin, CK and EKG 2-3 days. If troponin and labs normalize may resume therapy. If labs worsen or symptoms develop then treat as below. Hold pending evaluation
Grade >2 with suspected myocarditis	Hold dose.** Admit to hospital. Cardiology consult. Rule out MI and other causes of cardiac disease. Cardiac Monitoring. Cardiac ECHO. Consider cardiac MRI and cardiac biopsy. Initiate high dose methylprednisolone. If no improvement within 24 hours, add either infliximab, ATG or tacrolimus. Resume therapy if there is a return to baseline and myocarditis is excluded or considered unlikely.
Grade ≥2 with confirmed myocarditis	Off protocol therapy. Admit to CCU (consider transfer to nearest Cardiac Transplant Unit). Treat as above. Consider high dose methylprednisolone Add ATG or tacrolimus if no improvement. Off treatment.

^{*}Including CHF, LV systolic dysfunction, myocarditis, CPK, and troponin

Note: The optimal treatment regimen for immune-mediated myocarditis has not been established. Since this toxicity has caused patient deaths, an aggressive approach is recommended.

Skin Rash and Oral Lesions	Management/Next Dose for Nivolumab and Combination
≤ Grade 1	No change in dose.* Manage as clinically indicated.
Grade 2	Hold* until 1≤ Grade resolved^. Consider steroid treatment > 7 days. Resume at same dose level.

^{**}Patients with evidence of myositis without myocarditis may be treated according as "other event"

Skin Rash and Oral Lesions	Management/Next Dose for Nivolumab and Combination
Grade 3	$Hold*$ until \leq Grade 1. Resume at same level at investigator discretion.
Grade 4	Off protocol therapy.

^{*}Participants with purpuric or bullous lesions must be evaluated for vasculitis, Steven-Johnson syndrome, TEN, and autoimmune bullous disease including oral lesions of bullous pemphigus/pemphagoid. Pruritus may occur with or without skin rash and should be treated symptomatically if there is no associated liver or GI toxicity. Note skin rash typically occurs early and may be followed by additional events particularly during steroids tapering.

Recommended management: AE management guidelines (Appendix X).

Liver Function (AST, ALT, Bilirubin)	Management/Next Dose for Nivolumab and Combination
≤ Grade 1	Continue protocol therapy.
Grade 2	Hold until UNL or baseline. Resume at same dose level. Consider steroid treatment if > 7 days.
Grade 3	Discontinue protocol therapy if occurring before cycle 5. Initiate IV or PO steroids. May begin nivolumab monotherapy if returns to grade 1 off steroids by week 8 (no earlier than week 6). Hold protocol therapy if occurring after cycle 5. Initiate IV or PO steroids. If not returned to grade 1 off steroids by 6 weeks from missed dose, then off protocol therapy.
Grade 4	Off protocol therapy. Initiate IV steroids.

Continued treatment of active immune-mediated hepatitis may exacerbate ongoing inflammation. Holding drug to evaluate LFT changes, and early treatment are recommended. LFT changes may occur during steroid tapers from other events and may occur together with other GI events including cholecystitis/pancreatitis.

Recommended management: see Hepatic AE management algorithm (Appendix X).

Renal Toxicity	Management/Next Dose for Nivolumab and Combination
≤ Grade 1	No change in dose.
Grade 2	Hold until \leq Grade 1. Resume at same dose level. Steroid treatment if > 7 days.
Grade 3	Hold until ≤ Grade 1. Resume at same dose level.
Grade 4	Off protocol therapy.
Recommended management: see Renal AE management algorithm (Appendix X).	

Diarrhea/Colitis	Management/Next Dose for Nivolumab and Combination
≤ Grade 1	Hold until Grade 0 (if Grade 1) or baseline^. No change in dose.
Grade 2	Hold until Grade 0 or baseline. Steroid treatment if > 7 days
Grade 3	Off protocol therapy, may begin nivolumab monotherapy if resolved to grade 0 (or baseline) by week 16. If occurs during nivolumab monotherapy, then participant is off protocol therapy.
Grade 4	Off protocol therapy

See GI AE Algorithm for management of symptomatic colitis.

Participants with \leq grade 2 toxicity resolving to baseline within 7 days in the absence of steroids may resume with omitted dose and have treatment schedule postponed 1 week.

Participants with grade 2 symptoms but normal colonoscopy and biopsies may be retreated after resolution.

Participants who require steroids should be taken off study treatment if occurring before cycle 5.

Please evaluate pituitary function prior to starting steroids, if possible, without compromising acute care.

Evaluation for all participants for additional causes includes *C. diff*, acute and self-limited infectious and food borne illness, ischemic bowel, diverticulitis, and IBD.

Recommended management: see GI AE management algorithm (Appendix X).

Pancreatitis Amylase/Lipase	Management/Next Dose for Nivolumab and Combination
≤ Grade 1	Continue protocol therapy if asymptomatic.
Grade 2	Continue protocol therapy if asymptomatic.
Grade 3	Continue protocol therapy if asymptomatic at investigator's discretion.
Grade 4	If asymptomatic, hold the rapy until \leq grade 2, then resume at same dose level

Participants may develop symptomatic and radiologic evidence of pancreatitis as well as DM and DKA. Lipase elevation may occur during the period of steroid withdrawal and with other immune-mediated events or associated with colitis, hepatitis, and participants who have asymptomatic lipase elevation typically have self-limited course and may be retreated. For treatment management of symptomatic pancreatitis please follow the Hepatic Adverse Event Management Algorithm (Appendix X).

Pneumonitis	Management/Next Dose for Nivolumab and Combination
≤ Grade 1	Hold dose pending evaluation and resolution to \leq grade 0 or baseline including baseline pO ₂ . Resume no change in dose after pulmonary and/or ID consultation

Pneumonitis	Management/Next Dose for Nivolumab and Combination
Grade 2	Hold dose pending evaluation. Resume no change in dose after pulmonary and/or ID consultation if lymphocytic pneumonitis is excluded. Off study if steroids are required. ^
Grade 3	Hold dose pending evaluation. Resume no change in dose after pulmonary and/or ID consultation only if lymphocytic pneumonitis is excluded. Otherwise, off protocol therapy
Grade 4	Off protocol therapy

Distinguishing inflammatory pneumonitis is often a diagnosis of exclusion for participants who do not respond to antibiotics and have no causal organism identified including influenza. Most participants with respiratory failure or hypoxia will be treated with steroids. Bronchoscopy may be required and analysis of lavage fluid for lymphocytic predominance may be helpful. Participants with new lung nodules should be evaluated for sarcoid like granuloma.

Recommended management: See Pulmonary Adverse Event Management Algorithm (Appendix X).

Other GI N-V	Management/Next Dose for Nivolumab and Combination
≤ Grade 1	No change in dose.
Grade 2	Hold pending evaluation for gastritis duodenitis and other immune AEs or other causes. Resume at same dose level after resolution to \leq Grade 1.
Grade 3	Hold pending evaluation until \leq Grade 1. Resume at same dose level. If symptoms do not resolve within 7 days with symptomatic treatment participants should go off protocol therapy if occurring before cycle 5. May resume nivolumab monotherapy if resolved to \leq grade 1 (off of $>$ replacement steroids for 2 weeks by week 8)
Grade 4	Off protocol therapy.

Participants with grade 2 or 3 N-V should be evaluated for upper GI inflammation and other immune-related events.

Fatigue	Management/Next Dose for Nivolumab and Combination
≤ Grade 1	No change in dose.
Grade 2	No change in dose
Grade 3	Hold until ≤ Grade 2. Resume at same dose level.
Grade 4	Off protocol therapy

Fatigue is the most common AE associated with immune checkpoint therapy. Grade 2 or greater fatigue should be evaluated for associated or underlying organ involvement including pituitary, thyroid, and hepatic, or muscle (CPK) inflammation.

Neurologic Events	Management/Next Dose for Nivolumab and Combination
≤ Grade 1	Hold dose pending evaluation and observation. ^ If symptoms do not progress and processing below excluded may resume with no change in dose.*
Grade 2	Hold dose pending evaluation and observation. ^ Hold until ≤ Grade 1.* Off protocol therapy if treatment with steroids is required. ^ Resume at same dose level for peripheral isolated n. VII (Bell's palsy)^
Grade 3	Off protocol therapy
Grade 4	Off protocol therapy

^{*}Participants with any CNS events including aseptic meningitis, encephalitis, symptomatic hypophysitis, or myopathy, peripheral demyelinating neuropathy, cranial neuropathy (other than peripheral n. VII), GB syndrome, myasthenia gravis should be off study.

Recommended management: See Neurologic Adverse Event Management Algorithm ($\underline{\text{Appendix } X}$).

Endocrine Hypophysitis Adrenal Insufficiency	Management/Next Dose for Nivolumab and Combination
≤ Grade 1	Asymptomatic TSH elevation. Add hormone replacement as clinically indicated. Continue therapy.
Grade 2	Hold until participants are on a stable replacement hormone regimen. Resume at same dose level.
Grade 3	Hold until patients are on stable replacement hormone regimen. Resume at same dose level. If diagnosed with hypophysitis should hold therapy if occurring before cycle 5 but may begin nivolumab monotherapy when returned to grade 1 (no earlier than 6 week and by end of up to an 8-week delay).
Grade 4	Off protocol therapy

Note all participants with symptomatic pituitary enlargement, exclusive of hormone deficiency, but including severe headache or enlarged pituitary on MRI should be considered grade 3 events. Isolated thyroid or testosterone deficiency may be treated as grade 2 if there are no other associated deficiencies and adrenal function is monitored.

Please evaluate pituitary function before beginning steroid therapy or replacement therapy of any kind.

*Note participants with thyroiditis may be retreated on replacement therapy. Participants must be evaluated to rule out pituitary disease prior to initiating thyroid replacement.

Participants with symptomatic hyperthyroidism can be given a short course of a beta blocker (e.g., propranolol). Hyperthyroidism usually converts to hypothyroid within 4 weeks.

Recommended management: See Endocrine Management Algorithm (Appendix X).

Fever	Management/Next Dose for Nivolumab and Combination
≤ Grade 1	Antipyretic therapy if no evidence of infection.
Grade 2	Hold until ≤ Grade 1. Resume at same dose level.
Grade 3	Hold until ≤ Grade 1. Resume at same dose level.
Grade 4	Off treatment.

Participants with fever should be evaluated as clinically appropriate. Participants may experience isolated fever during infusion reactions or up to several days after infusion. Evaluation over the course of 1-2 weeks should be done for other autoimmune events that may present as fever.

See Section 4.12, infusion reactions.

HIV Viral Load Increase	Management/Next Dose for Nivolumab and Combination
>1,000 on two consecutive readings	Strongly consider modifying HAART therapy, preferably after consulting an HIV specialist.

Treatment with steroids may be initiated at any time if clinically indicated; recommended delayed dosing for evaluation is not mandatory.

Participants on single agent therapy requiring a delay of > 35 days must be permanently discontinued from study therapy, except as specified in Section 4.10 (Criteria to Resume Treatment).

Participants on combination therapy requiring a delay of > 42 days (> 56 days for participants on high dose steroids with required 4 weeks minimal taper and 2-week observation) should go off protocol therapy.

Participants requiring > two dose delays for the same event should go off protocol therapy.

Prior to starting corticosteroids or hormone replacement for any reason, appropriate endocrine testing including cortisol, ACTH, TSH and T4 must be obtained to document baseline.

Participants may be dose-delayed for evaluation and restarted depending on results.

Any participant started on corticosteroids initially who is determined to not require steroids treatment for an autoimmune AE may resume therapy after a 2-week observation period without further symptoms at the discretion of the PI or investigator.

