4.6.4 Precautions

Combination therapy may result in unexpected toxicity especially in novel combinations with other immune modifying agents. A striking example in macaques is presented in Vaccari, *et al.* 2012.

Please note that while unproven, there is a suggestion that autoimmune events, including hepatitis, may occur more frequently at sites of metastases or prior injury.

Caution is advised when considering treatment with high dose IL-2 in participants who have previously been administered ipilimumab, particularly in participants who experienced ipilimumab-related diarrhea/colitis. Colonoscopy or sigmoidoscopy with biopsy may be advisable prior to IL-2 administration once the participant is no longer receiving ipilimumab.

Participants who have received ipilimumab may potentially develop autoimmune disease with subsequent therapy including the appearance of colitis, hypophysitis, or adrenal insufficiency.

4.7 **Duration of Therapy**

In the absence of treatment delays due to AE(s), treatment may continue 92 weeks of nivolumab (with ipilimumab, if receiving dose level 2 or -2) until one of the following criteria applies:

• The development of progression (confirmed PD by RECIST Criteria or PD by the KS evaluation criteria in Section 9.2 or per Section 9.3, utilizing the consensus RECIL (2017). Participants will remain on study treatment until progression is confirmed,

Pregnancy

- All WOCBP should be instructed to contact the investigator immediately if they suspect they might be pregnant (e.g., missed, or late menstrual period) at any time during study participation. Institutional policy and local regulations should determine the frequency of on study pregnancy tests for WOCBP enrolled in the study.
- o The investigator must immediately notify CTEP in the event of a confirmed pregnancy in a study participant.
- Intercurrent illness that prevents further administration of treatment.
- Unacceptable AE(s) which include the following (see also Section 6.0 and specific algorithms in Appendix X):
 - o Any grade 4 events except as noted below.
 - o Grade 3 drug-related autoimmune or inflammatory events including uveitis, pneumonitis, diarrhea, colitis, neurologic AEs, hypersensitivity reaction, or infusion reaction of any duration requires discontinuation except as noted below:
 - o Any other grade 3 non-skin, drug-related AE lasting >7 days including fatigue.

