 - o Any grade 3 or 4 drug-related laboratory abnormality or electrolyte abnormality,

- not associated with underlying organ pathology that does not require treatment except for electrolyte replacements **does not** require treatment discontinuation.
- o Grade 3 or 4 amylase or lipase abnormalities that are not associated with DM, associated liver or gall bladder inflammation clinical manifestations of pancreatitis and which decrease to ≤ Grade 2 within 1 week of onset **may** resume study treatment when resolved.
- Any grade 2 drug-related uveitis or eye pain or blurred vision that does not respond to topical therapy and does not improve to Grade 1 severity within the re-treatment period OR requires systemic treatment.
 - Participants requiring > two dose delays for the same type of event should go off protocol therapy.
 - Any AE, laboratory abnormality, or intercurrent illness, which, in the judgment of the investigator, presents a substantial clinical risk to the participant with continued study drug dosing.
- Any participants who require additional immune suppressive treatment beyond steroids should go off study treatment.
- In participants with HIV-cHL, any participant who requires consolidative therapy with high dose chemotherapy followed by stem cell transplantation will be permitted to go off study therapy.
- Withdrawal of informed consent (participant's decision to withdraw for any reason).
- General or specific changes in the participant's condition, or any clinical AE, laboratory abnormality or intercurrent illness, which, in the opinion of the investigator, indicate that continued treatment with study therapy is not in the best interest of the participant.
- Termination of the study by sponsor.
- Participants treated with systemic steroids, except for a short course of tapered steroids for grade 3 rash and physiologic replacement doses, should be off study.
 - Participants who have been treated with steroids and who do not have an immunologically based event (e.g., infectious pneumonia rather than lymphocytic pneumonitis) may be restarted on treatment if asymptomatic after 2 weeks off all steroids.
 - o Tumor assessments should continue as per protocol even if dosing is interrupted.

4.8 **Duration of Follow-Up**

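### The suspected-myocarditis row in Section 5.1 allows re-dosing after second-line immunosuppression or a grade 4 event, although Section 4.7 stops treatment in both cases

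*Combined protocol and SAP*

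**What the plan says.** **The row.** Section 5.1, Table 2 (Cardiac) deals with suspected myocarditis above grade 2 by holding the dose, admitting the participant, obtaining a cardiology work-up and giving high-dose methylprednisolone. If there is no improvement within 24 hours, the instruction is to "add either infliximab, ATG or tacrolimus. Resume therapy if there is a return to baseline and myocarditis is excluded or considered unlikely". The next row takes confirmed myocarditis off protocol therapy. A note under the table says this toxicity has caused deaths.

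**The stopping rules.** Under Section 4.7 (Duration of Therapy), treatment continues "until one of the following criteria applies". The criteria include "Any grade 4 events except as noted below" and, separately, "Any participants who require additional immune suppressive treatment beyond steroids should go off study treatment". Section 4.9 provides for removal when criteria listed in Section 4.7 are met. Section 4.10 opens by confining restarts to grade 2 events and some grade 3 events, naming skin rash and thyroiditis.

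**Precedence.** The one ranking rule is in Section 5.1: "Where discrepancies occur between Section 5.1 and Appendix X, use the instructions in Section 5.1". It does not mention Sections 4.7, 4.9 or 4.10.

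**The concern.** The resume sentence comes directly after the second-line agents, so it reads as applying to participants who received them. It also covers grade 4, because the row has no ceiling. Section 4.7 stops both groups. A site working from the table could give checkpoint therapy again to someone the protocol elsewhere takes off treatment, after an event managed as possible myocarditis.

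Sites have reason to work from the table. Section 4.1 points to Section 5.0 and Appendix X for dose modifications, and Section 5.2 says management decisions should rest on Section 5.1, Appendix X and the investigator's brochure. Neither names Section 4.7. The title of Appendix X lists no cardiac algorithm, so this table is the protocol's specific cardiac instruction.

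**Working it through.** No figure in the plan needs reproducing. The check sets the texts side by side for participants who return to baseline with myocarditis excluded or judged unlikely.

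| Case | Section 5.1 row | Section 4.7, applied through 4.9 | Opening sentence of 4.10 |
|---|---|---|---|
| A. Grade 3, steroids only | Resume | Off, unless the event is not immune-based and the participant is asymptomatic after 2 weeks off all steroids | Grade 3 restart named only for rash and thyroiditis |
| B. Grade 3, infliximab, ATG or tacrolimus given | Resume | Off, no exception stated | As for A |
| C. Grade 4, treated as the row directs | Resume | Off, no listed exception fits | Grade 4 not included |
| D. Grade 4, isolated laboratory rise without organ pathology, needing no treatment beyond electrolytes | Resume | Laboratory exception may apply | Grade 4 not included |

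**Cases B and C** contradict Section 4.7 outright. **Case A** can be reconciled with Section 4.7, but only under the steroid-free condition, which the row does not state. **Case D** may be no conflict with Section 4.7. The suspected row prints its threshold as above grade 2 and the confirmed row as grade 2 or higher. Grade 4 is covered either way.

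**Do the exceptions in Section 4.7 rescue the row?** The laboratory exception requires no organ pathology and no treatment beyond electrolyte replacement, so a participant given methylprednisolone for suspected myocarditis falls outside it. The other grade 4 exception concerns "Grade 3 or 4 amylase or lipase abnormalities that are not associated with DM" and is not cardiac. The restart allowance for events that prove not to be immune covers "Participants who have been treated with steroids and who do not have an immunologically based event". It names steroids only, as does the similar allowance at the end of Section 5.1.

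**Grade 4 across Table 2.** There are 14 graded event tables: other non-immune, other immune, cardiac, skin, liver, renal, diarrhea/colitis, pancreatitis, pneumonitis, other GI, fatigue, neurologic, endocrine and fever. Twelve take grade 4 off therapy. Pancreatitis lets asymptomatic grade 4 resume and has a related amylase/lipase exception in Section 4.7. That leaves 14 − 12 − 1 = 1, the cardiac table, whose suspected row has neither a grade 4 stop nor a cardiac exception in Section 4.7.

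**DLT count, as a remote illustration.** Section 4.4 makes a permanent stop within 6 weeks of the first dose a DLT. Section 4.2 tolerates at most 1 DLT in 6 (16.7%), and a second exceeds the MTD (2/6 = 33.3%). In a cohort with one DLT already, a related event of type B or C could leave 1/6 if the participant resumed or make 2/6 if Section 4.7 were applied. This requires the event to fall within 6 weeks, to remain at least possibly related although myocarditis is excluded or unlikely, and to occur in a cohort still under DLT evaluation with exactly one prior DLT.

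**The case against.** The best answer is that the rules are cumulative: the row permits resumption only if no Section 4.7 criterion has been met. Section 4.9 supports this by tying removal to Section 4.7 with no carve-out for Table 2, and the opening of Section 4.10 is a second bar to restarting after grade 4. A reader might infer that the protocol leaves the matter evenly open. It does not: three sections point towards stopping, so the row is the defective text. That part of the objection stands. It does not remove the conflict, because none of the three is said to prevail over Section 5.1.

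It can also be argued that someone in whom myocarditis is excluded never truly required the second-line agent. Nothing in the documents says so, and the written restart allowances stop at steroids.

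The grade 4 tally is modest support, since the cardiac table is organised by suspected versus confirmed disease. A reader might also compare the grade 3 pneumonitis row, which demands exclusion of the immune cause, and infer that accepting an unlikely diagnosis is itself an error. That is a clinical threshold choice and is not part of this point.

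Safeguards exist: expedited reporting (Section 6.3.3), medical monitor review (Appendix VI), the investigator's right to stop dosing (Section 4.7), and delay limits of 35, 42 or 56 days (Sections 4.5, 4.10 and 5.1). They lower the chance of unsafe re-dosing but do not say which instruction governs.

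**Conclusion.** The contradiction holds for two groups: participants given immunosuppression beyond steroids, and participants with grade 4 events outside the Section 4.7 laboratory exceptions. Steroid-treated grade 3 cases are a lesser gap, because the row omits the conditions under which Section 4.7 would let them restart.

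The group should be small. The documents give no rate for suspected myocarditis, for second-line use or for later exclusion of the diagnosis, so no number can be put on it. The conclusion assumes that sites take the row as written.

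Two stronger readings are not supported. A reader might infer that confirmed myocarditis can be rechallenged, but the next row takes it off therapy. A reader might also infer that the MTD determination is in doubt. The required coincidence of events is remote. DLTs are discussed by the chairs, the Phase I Committee chair, the medical monitor and the biostatistician (Section 4.4), and Appendix VI has the protocol chair, medical monitor and statistician decide whether the dose rules are met. Section 2.3.9 also reports that dose level 2 was already found tolerable in Stratum 1.

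The row should be corrected because it is a re-dosing instruction for a toxicity that the protocol itself describes as having killed patients.

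**What to change.** Keep the row's two existing conditions (return to baseline, and myocarditis excluded or thought unlikely) and add three more, all of which must hold before therapy resumes:

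- *The event was below grade 4, apart from the Section 4.7 laboratory exceptions.*
- *No immunosuppression beyond steroids was given.*
- *If steroids were given, the event is judged not to be immunologically based and the participant has no symptoms after 2 weeks off all steroids, as Section 4.7 requires.*

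End the clause with: *All others go off protocol therapy under Sections 4.7 and 4.9.* The third condition is needed so that the correction does not endorse restarting steroid-treated grade 3 cases that Section 4.7 would stop. Align the first sentence of Section 4.10 with the amended row, since as it stands it names only rash and thyroiditis at grade 3.

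The cost is one table entry and one sentence in the next amendment. A few participants in whom myocarditis is later excluded would lose further treatment. If the clinical team wants to keep them on treatment, it should instead write a cardiac exception into Section 4.7 and align Section 4.10 with that.
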